## EXECUTIVE SUMMARY - CHANGE IN STUDY DESIGN IN PROTOCOL VERSION 7.0

Protocol version 7 reflects a change in the study design. Prior versions of the protocol included a Phase Ib (Part A) - a dose-escalation phase to assess safety, tolerability and preliminary biological effects of CLS12311, followed by a Phase II (Part B), aiming to extend the safety dataset and gather proof-of-concept for efficacy of the treatment. The Sponsor has decided not to initiate the Phase II (Part B) study. This decision is not based on a change in the risk-benefit assessment.

The current protocol version has therefore been amended to indicate that the study will conclude after completion of Phase Ib (Part A) only.

## 2 ABBREVIATIONS AND DEFINITIONS

AE	Adverse Event
AESI	Adverse Event of Special Interest
AIDS	Acquired Immunodeficiency Syndrome
ALT	Alanine Aminotransferase
APC	Antigen-Presenting Cell
AR	Adverse Reaction
AST	Aspartate Aminotransferase
BL	Baseline visit
BMI	Body Mass Index
BP	Blood Pressure
CD	Cluster of Differentiation
CEL	Contrast-Enhancing Lesion
CK	Creatin Kinase
ClinO	Ordinance on Clinical Trials in Human Research
CNS	Central Nervous System
eCRF	electronic Case Report Form
CRO	Clinical Research Organization
CRP	C-reactive Protein
CSF	Cerebrospinal Fluid
CSR	Clinical Study Report
CTCAE	Common Terminology Criteria of Adverse Events
CTR	Clinical Trials Regulation (EU) No. 536/2014
DMT	Disease Modifying Therapy
DSMB	Data Safety Monitoring Board
DTH	Delayed Type Hypersensitivity
EAE	Experimental Autoimmune Encephalomyelitis
EBV	Epstein Barr Virus
ECG	Electrocardiogram
EDC	1- Ethyl- 3- (3-Dimethylaminoprpyl) – carbodiimide
EDSS	Expanded Disability Status Scale
EDTA	Ethylene Diamine Tetra-Acetate
ED	Early Discontinuation
eGFR	Estimated Glomerular Filtration Rate
EMA	European Medicines Agency
EOT	End of Treatment
EOS	End of Study

ETIMS	Establish Tolerance in MS
FS	Functional System
GBCA	Gadolinium-based contrast agent
GCP	Good Clinical Practice
GDPR	General Data Protection Regulation
GFR	Glomerular Filtration Rate
GGT	Gamma-Glutamyltransferase
GMP	Good Manufacturing Practice
GOT	Glutamat-Oxalacetat-Transaminase
GPT	Glutamat-Pyruvat-Transaminase
HED	Human Equivalent Dose
HIV	Human Immunodeficiency Virus
HLA	Human Leukocyte Antigen
HLA-DR	Human Leukocyte Antigen Class II
9-HPT	Nine Hole Peg Test (clinical test for hand function)
HR	Heart Rate
ICF	Informed Consent Form
ICH	International Conference on Harmonisation
ID	(Patient) Identification
IEC	Independent Ethics Committee
IFN	Interferon
IL	Interleukin
IMP	Investigational Medicinal Product
INR	International Normalized Ratio
IRB	Institutional Review Board
IRTS	Interactive Response Technology System
ISF	Investigator Site File
ITT	Intent-To-Treat
i.v.	Intravenous
MBP	Myelin Basic Protein
MOG	Myelin Oligodendrocyte Glycoprotein
MRI	Magnetic Resonance Imaging
MS	Multiple Sclerosis
MSFC	Multiple Sclerosis Functional Composite
NA	Not Applicable
NFL	Neurofilament Light Chain
p-value	Probability value
PBMC	Peripheral Blood Mononuclear Cells

pH	Value potential Hydrogenium-Value
PLP	Proteolipid Protein
PP	Per Protocol
PT	Prothrombin Time
PTT	Partial Thromboplastin Time
PV	Pharmacovigilance
PVE	Polypropylene/Vinyl Ethylene Acetate
RAB	Relapse Assessment Board
RASGRP	RAS Guanyl Releasing Protein
RBC	Red Blood Cells
RR	Relative Risk
RRMS	Relapsing-Remitting Multiple Sclerosis
SAE	Serious Adverse Event
SAF	Safety Analysis Set
SAP	Statistical Analyses Plan
SAR	Serious Adverse Reaction
SD	Standard Deviation
SDMT	Symbol Digit Modalities Test (cognitive test)
SJL mice	Swiss James Lambert mice
SFU	Safety Follow Up
SOP	Standard Operating Procedure
SP	Secondary Progressive
SUSAR	Suspected Unexpected Serious Adverse Reaction
T cell	T lymphocyte cell
TCC	T Cell Clone/s
TEAE	Treatment Emergent Adverse Event
TESAE	Treatment Emergent Serious Adverse Event
T25-FW	Timed 25-Foot Walk Test
TMF	Trial Master File
TSTA3	Tissue Specific Transplantation Antigen 3, also known as GDP L-fucose synthase
WCS	Worst Case Scenario

### 3 PROTOCOL SUMMARY / SYNOPSIS

Study title	Multicenter, Phase Ib/Ila Study on the Safety and Efficacy of Autologous Peptide-coupled Red Blood Cells in Patients with Relapsing Remitting Multiple Sclerosis
Brief study title	Peptide-coupled Red Blood Cells for the Treatment of Multiple Sclerosis
Acronym	RED4MS
Version Number	7.0
Version Date	2025-05-09
Development phase	Phase Ib
Study No.	MSB-IG-H-2101
EU-CT No.	2023-510127-30-00
Study drug	Peptide-coupled red blood cells (CLS12311)
Coordinating Investigator	
████████████████████
 
████████████████████
 
██
 
████████████████████
 
████████████████████████████
 
████████████████████████████████

Sponsor	Cellerys AG [name]  EU legal representative: SCOPE International [name]
CRO	SCOPE International [name] [contact] E-Mail: [contact]
Study design	Phase Ib open-label trial evaluating ascending-doses of CLS12311  Note: Originally, the study was designed to include a Phase IIa part (Part B). The Phase IIa (Part B) will not be conducted. This amendment reflects the adjustment to a Phase Ib only design.
Study objectives	Safety Objective Primary safety objective: 

To assess the safety and tolerability of CLS12311 in patients with relapsing remitting multiple sclerosis (RRMS)

 Secondary safety objective: 

To assess the safety and tolerability of each dose group of CLS12311

 Exploratory objective 

To understand the mechanism/s of action of tolerance induction with peptide-coupled RBCs and to identify biomarkers for measuring immune tolerance induction

Primary endpoint	Safety endpoint 
 
Safety and tolerability of CLS12311 measured by the number and severity of treatment-emergent adverse events (TEAEs) and treatment emergent serious adverse events (TESAEs) and/or worsening of disease by clinical (relapses) and imaging (number and size of brain MRI lesions)
 
 
MRIs will be assessed centrally by independent readers.

Secondary endpoints	Safety endpoints 
 
Number and severity of TEAEs and TESAEs in each dose group
 
Number of confirmed relapses in the treatment phase in each dose group
 
Changes in clinical measures of disease severity (EDSS, 9-HPT, T25-FW, SDMT) following CLS12311 administration in each dose group
 

Exploratory endpoints	Exploratory immunological and biomarker measures 
 
Percentage of patients in each dose group showing a reduction of antigen-specific T cells against the protein(s) they responded to at the study entry
 
Changes in predefined serum- and cellular biomarkers including autoantigen-specific T cell responses that would indicate proinflammatory activation
 

Study plan	
Multicenter, open-label, dose-escalation Phase Ib trial evaluating the safety and tolerability of intravenous CLS12311 in subjects with RRMS.
 
Eligibility will be assessed during baseline (week 0), when general patient and disease characteristics will be recorded. Patients who meet the criteria for enrollment will be sequentially allocated to one of the dose groups. The allocation to the dose group and timing of treatment administration will be coordinated centrally.
 
All enrolled patients will be followed for at least 48 weeks, with visits as outlined in the Schedule of Events -Table 4.1.
 
Open Label Treatment Phase: at least 17 weeks
 
Single treatment cycle
 
The safety and tolerability of a single treatment cycle of CLS12311 will be assessed in an open label, ascending dose study over three dose groups in a total of 9 patients. Patients will be allocated to a low (total dose [REDACTED]; n=2), medium (total dose [REDACTED]; n=3) or high dose (total dose [REDACTED]; n=4). Each dose group will start with a sentinel patient. The treatment will start with the lowest dose group. Further dosing in the higher dose groups will only be initiated if, in the preceding dose group, safety based on (S)AEs and relapses until visit 5 has been confirmed by Sponsor's medical expert(s). To ensure the safety of dosing in the subsequent patient, a minimum time interval of four days will be established prior to dosing the next patient. The DSMB will evaluate all safety data of the ascending dose study after the last patient in Part A has completed the [REDACTED]
 
Second treatment cycle
 
The safety and tolerability of a second treatment cycle of CLS12311 will be investigated in a subgroup of patients (n=6) from the initial ascending dose study of the first treatment cycle. The sentinel patients will not receive a second treatment cycle. All other patients will remain in the same dose group and receive a second treatment cycle of [REDACTED] (n=1), [REDACTED] (n=2) or [REDACTED] (n=3) at [REDACTED] of the study. Thus, patients receiving a second treatment cycle will have the following total product exposure: low dose group 6x10^11 (n=1), medium dose group [REDACTED] (n=2) or high dose group [REDACTED] (n=3).

The second treatment cycle will only be administered after verifying the safety of the first treatment cycle given to the first patient in the next higher dose group, has been confirmed in [REDACTED]. Only after confirmation of the tolerability and safety of the treatment in **patient 3** (single dose of [REDACTED]) in [REDACTED], the second treatment cycle of patient 2 (total cumulative dose of [REDACTED]) will be permitted. Patients 4 and 5 will receive second treatment (total cumulative dose of [REDACTED]) only if the week 7 safety data of **patient 6** (single dose of [REDACTED]) will support a second dosing of CLS12311.

Information on the safety of the second treatment cycle in patient 2 will be available prior to administration of the second treatment in patients 4 and 5, as the information of the safety of the second treatment cycle in patient 4 or 5 will be available prior to dosing of the second treatment cycle in patients 7 - 9. In patients who received at least one dose of study drug and prematurely discontinue treatment period and/or choose not to stay in the study until the [REDACTED], a study visit according to the early discontinuation (ED) will be performed.

After the last patient in the high dose group has completed [REDACTED] the safety data (including MRI data, relapses and EDSS) from all patients will be evaluated by the DSMB.

**Safety Follow Up:** approximately 31 weeks

At the completion of the treatment phase at [REDACTED], patients will enter a safety follow up (SFU) of 31 weeks. During the safety follow up period patients will be assessed as per Schedule of Events - Table 4.1. Patients who discontinue the safety follow-up phase and their last visit has been more than 8 weeks ago, shall perform a study visit according to early discontinuation (ED) visit.

**Withdrawal Criteria**

Patients must be withdrawn from the study under the following circumstances:

- Pregnancy detected at any time during the study. Pregnancy in patients who become pregnant after the first study dose will be followed until delivery. Patients may volunteer further information regarding child health at 12 months after birth
- A positive result in the infectious disease screen analyzed according to local regulations during eligibility testing and/or release of autologous RBC donation.
- The patient withdraws consent
- Patient takes any of the drugs mentioned under exclusion criterion No. 2 (except for relapse treatment as outlined in section 11.2 of the study protocol)
- The patient is unable or unwilling to comply with the protocol
- Any other disease or condition which could interfere with the participation in the study according to the study protocol, or with the ability of the patients to cooperate and comply with the study procedures
- Any medical condition, which the physicians and Investigators deem severe or compromising regarding the safety of the patient and/or the study results, e.g. disease progression requiring the use of effective MS treatment (DMT)

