Given the excellent tolerability of peptide-coupled RBCs so far, and the safety-focused design of this Phase I trial, the potential benefits of the expanded peptide pool and increased dose are well balanced to the risks of this development step. To support patient safety, comprehensive safety measures are in place, including regular monitoring during and after infusion, immediate access to supportive care for managing any adverse effects, and thorough eligibility assessments.

Detailed information about the known and expected benefits and risks and reasonably expected adverse events (AEs) of CLS123 is provided in the latest version of the Investigator's Brochure and informed consent form (ICF). The COVID19 pandemic has brought additional uncertainties and risks, particularly to patients with long-term immunosuppressive therapies and thereby increasing the burden of disease considerably. A treatment regimen aiming at induction of antigen-specific immune tolerance and sparing the protective immune responses, might reduce this burden and improve the reactivity to the pathogen and/or a vaccine, aiming to prevent an infection.

Patients participating in the RED4MS trial will remain off immunosuppressive therapies for the duration of the trial. The treatment with CLS12311 is not expected to interfere with an antiviral immune response. Hence participation in RED4MS trial is not expected to increase the risks associated with SARS-CoV-II infection.

The COVID19 pandemic is rapidly evolving requiring flexibility in adapting measures to ensure the safety and well-being of trial participants and the integrity of the trial. During the conduct of the trial all measures will be taken, according to national recommendations and local regulations, to reduce the risk of viral transmission and infection of trial participants. The Sponsor will follow regulatory guidance relevant to the management of the clinical trial in the COVID19 pandemic. The Sponsor together with Steering Committee of the trial will assess the situation on a regular basis and implement any necessary safety measures.

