**Figure 7-1    Patients’ enrollment and safety assessments in the treatment phase**

## 7.2 Safety Follow Up Phase: approx. 31 weeks

At the completion of the treatment phase, patients will enter a 31-week safety follow up (SFU) period, including three visits: three weeks after the end of the treatment period (Week 20), at Week 24 and at Week 48.

During the SFU, patients will be assessed at clinical visits as per Schedule of Events – please refer to Table 4.1 for further details.

The DSMB will reconvene after the completion of [REDACTED] to assess the safety outcomes of the trial.

[figure not shown]
If patients wish to discontinue the unblinded SFU and the last visit has been more than 8 weeks ago, they should be invited for an ED visit to capture safety data and ensure continued patient monitoring.

As the duration of the treatment effect is not known, patients may begin another DMT during the SFU, at the discretion of the investigator. However, every effort should be made to have patients complete the SFU and all related assessments, regardless of whether or not they receive alternative treatment for their MS.

In summary, this Phase Ib trial is designed to provide a maximum of safety throughout both single dose escalation and second treatment cycle.

Safety data will be evaluated by a DSMB after key milestones to assess the overall safety of CLS12311 and the different dose levels tested. A brief overview of the course of the Phase Ib study is shown in Figure 7-2.

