### 9.3.3 Discontinuation Criteria Related to the Patient

The patients will be advised in the Informed Consent Forms that they have the right to withdraw from the study at any time without prejudice and may be withdrawn at the Investigator's / Sponsor's discretion at any time.

Withdrawal of individual patients from treatment or from the study respectively is caused by (but is not limited to) the following reasons:

- Pregnancy detected at any time during the study.
- At the discretion of the Investigator
- Disease progression requiring the use of effective MS treatment (DMT)
- Major protocol deviation(s)
- Ineligibility/Development of one or multiple protocol-specified withdrawal criteria
- Adverse Event
- At the specific request of the sponsor
- The patient withdraws of consent
- Lost to follow-up

In case a patient does not reappear to any scheduled visit (i.e. is lost to follow-up) reasonable effort should be made to contact this patient in order to complete assessments and/or to evaluate the reason for non-appearance (possibly implicit withdrawal of consent). These contact attempts

should be documented in the medical records. Should the patient continue to be unreachable, he/she will be considered to have withdrawn from the study with a primary reason of lost to follow-up.

In the event that a patient withdraws consent or is withdrawn from the study, the study termination page in the (e)CRF should be completed indicating that the study was prematurely terminated. The Investigator should record the date of the withdrawal and the reason for withdrawal.

If a subject wishes to withdraw his/her consent to the testing of his/her samples, the Investigator must inform the Sponsor in writing of the subject's wishes and enter the date of withdrawal in the subject's electronic Case Report Form (eCRF).

Patients who received at least one dose of CLS12311 and prematurely discontinue the treatment phase stay in the study and follow the schedule of assessments in the treatment phase. If a patient withdraws from the study, the patient should be encouraged to return for the ED visit (see section 14.1.9) and asked if he or she can still be contacted for further information. The outcome of that discussion should be documented in both the medical records and in the eCRF.

Female patients with a suspected unplanned pregnancy during the study must permanently discontinue the study, contact their study investigator to confirm the pregnancy by urine pregnancy testing.

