### 11.1 Therapies not allowed during the Study

Any of the drugs mentioned under Exclusion Criterion No. 2 (see Section 8.1.2) will not be allowed during the study.

Patients may not receive systemic corticosteroid therapy except for the treatment of relapses (see section 11.2).

Patients may not receive any other investigational product including investigational symptomatic therapies for MS and investigational therapies for non-MS indications.

In the Safety Follow Up period there are no restrictions regarding concomitant medication.

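### The synopsis requires study withdrawal for taking any exclusion-2 drug, with no limit to the treatment phase, although the protocol body permits a DMT in the safety follow-up and wants the follow-up completed

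*Protocol*

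**What the plan says.** **Synopsis (Protocol section 3, Withdrawal Criteria).** The list opens with "Patients must be withdrawn from the study under the following circumstances". One item is "Patient takes any of the drugs mentioned under exclusion criterion No. 2", with section 11.2 relapse treatment as its sole exception. The last bullet covers severe medical conditions and gives progression requiring a DMT as its example. Neither item names a study phase.

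**Section 9.3.3.** The reasons for withdrawal from treatment or from the study include progression requiring a DMT, and also "Ineligibility/Development of one or multiple protocol-specified withdrawal criteria". The exclusion-2 item itself is not repeated there.

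**Section 7.2.** In the safety follow-up (SFU), "patients may begin another DMT during the SFU, at the discretion of the investigator". Every effort is to be made to have patients complete the SFU "regardless of whether or not they receive alternative treatment for their MS".

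**Section 11.1.** Exclusion-2 drugs "will not be allowed during the study", but the section closes with "In the Safety Follow Up period there are no restrictions regarding concomitant medication".

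**SAP 5.3.** DMTs used in the SFU are to be entered in the eCRF, and medications started in that phase form a separate post-treatment class.

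**The concern.** A patient who uses the permission in section 7.2 also meets a mandatory criterion for leaving the study. The two instructions lead to opposite actions, and no text says which prevails. Section 9.3.3 refers to protocol-specified withdrawal criteria, and the only list under the heading Withdrawal Criteria is the one in the synopsis.

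Safety data are at stake. SAP 2.2.1 defines the primary endpoints (TEAEs, TESAEs, confirmed relapses, brain lesions) without a phase limit. The exposure-adjusted TEAE rates in SAP 5.5.1 run to the end of the SFU, and the annualized relapse rate in SAP 5.5.2 includes the SFU. There are 9 patients. A patient who starts a DMT is plausibly one with disease activity, so the missing follow-up would not be a random part of the data.

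**Working it through.** The plan gives no figure on this point, so the check is a comparison of texts followed by simple arithmetic on the most that could be lost.

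**Step 1: do the two rules cover the same drugs?** Protocol 5.1.1 names 15 approved MS therapies. In exclusion criterion 2 (section 8.1.2) they appear as follows:

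- item a: glatiramer acetate, interferon-beta (2)
- item b: dimethyl fumarate, diroximel fumarate (2)
- item c: teriflunomide (1)
- item d: fingolimod, ozanimod (2)
- item e: siponimod, ponesimod (2)
- item f: natalizumab (1)
- item g: ocrelizumab, ofatumumab, alemtuzumab, cladribine, mitoxantrone (5)

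2 + 2 + 1 + 2 + 2 + 1 + 5 = 15 of 15. Starting any of them in the SFU meets the synopsis item.

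**Step 2: follow-up time.** The SFU lasts 31 weeks after a 17-week treatment phase (Protocol 7.2 and 15.1), taking 48 weeks per patient.

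- Most that one patient can lose: 31/48 = 64.6%.
- Share of all planned person-weeks: 31/(9 × 48) = 31/432 = 7.2%.
- Share of a dose group's person-weeks: low 31/96 = 32%, medium 31/144 = 22%, high 31/192 = 16%.

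**Step 3: MRI.** SAP 5.5.3 has new/enlarging T2 counts at four scheduled time points. The visit labels are redacted there, but the MRI row in SAP section 1 lines up with the laboratory rows, which SAP 5.5.8 places at Visits 1, 7, 13, 15 and 16. The four counts therefore fall at Visits 7, 13, 15 and 16, and two of them (Visits 15 and 16) are in the SFU.

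**Step 4: what the early discontinuation (ED) visit recovers.** Section 14.1.9 requires it in the SFU only if the last visit was more than 8 weeks earlier. SFU visits are at Weeks 20, 24 and 48, so the requirement begins at about Week 24 + 8 = 32. No ED visit is required for leaving between Weeks 17 and 32, which is 15/31 = 48% of the SFU, although section 9.3.3 encourages one.

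| Time of leaving | Weeks lost (48 − week) | Scheduled T2 counts lost | ED visit required |
|---|---|---|---|
| Week 17 to before the Week 24 visit | 31 to 24 | 2 of 4 | no |
| After the Week 24 visit to Week 32 | 24 to 16 | 1 of 4 | no |
| After Week 32 | fewer than 16 | 1 of 4 | yes, with MRI unless one was done in the previous 2 weeks |

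**Step 5: what is not lost.** Data up to withdrawal are kept (section 9.3.1). Existing adverse events are followed until explained or until stopping is medically justified (13.2.1), and serious ones beyond the observation period (13.3). The secondary dose-group relapse endpoint counts the treatment phase only (SAP 2.2.2).

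**The case against.** The strongest reply is that the body text already settles the matter. Sections 7.2 and 11.1 are the specific rules for the SFU. The synopsis item reads naturally as the consequence of breaking the ban in 11.1, and that ban is lifted in the SFU. SAP 5.3 plans to collect DMT use in the SFU, which presupposes that patients on a DMT remain. Section 9.3.3 keeps dosed patients who stop the treatment phase in the study. All of this stands as evidence of intent. It does not remove a mandatory sentence whose author wrote one exception and no other.

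A reader might infer more than the documents support:

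- *That the plan means to withdraw these patients, or that 31 weeks will be lost.* Neither follows. The 31 weeks need a DMT start at the very beginning of the SFU and a site that puts the synopsis above sections 7.2 and 11.1.
- *That all adverse event follow-up would stop.* Only the collection of new events would.
- *That section 5.3 is a second prohibition.* It says patients "will remain off immunosuppressive therapies for the duration of the trial", but this is risk-benefit narrative about COVID-19 and refers to immunosuppressive therapies, while section 5.1.1 describes the approved drugs as immunomodulating and/or immunosuppressive.
- *That section 11.1 contradicts itself.* Its last sentence qualifies its first.

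It is also fair to say that relapse and lesion counts after a DMT start reflect that DMT as well as CLS12311, so the lost weeks are worth less than untreated follow-up.

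**Conclusion.** The inconsistency is real, and it lies in the wording. The design choice itself, a DMT permitted with continued follow-up, is sound. Read literally, the synopsis gives the wrong action for any patient who starts an approved DMT in the SFU, and the items on progression requiring a DMT have the same gap.

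The Step 2 and Step 3 losses are ceilings for a single such patient. The documents do not say how often a DMT would be started in the SFU, so no expected loss can be given. The shares assume exactly 48 weeks per patient and nominal visit weeks; the protocol says at least 48, so they are approximate.

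**What to change.** 1. In the synopsis, limit the exclusion-2 item and the DMT example in the last bullet to the treatment phase.
2. In section 9.3.3, limit the item on progression requiring a DMT to the treatment phase, as withdrawal from treatment.
3. State in the synopsis that starting a DMT in the SFU is not by itself a reason for study withdrawal and that, with the patient's consent, scheduled assessments continue to Visit 16.
4. Optionally align the sentence in section 5.3. Section 11.1 needs at most a cross-reference.

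The cost is wording in two places, subject to the amendment assessment in section 19.7. No visit or assessment is added.

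SAP Final 2.0 (03-FEB-2026) follows drafts updated after the Data Review, so conduct may already be complete and an amendment may affect no patient. In that case, state in the CSR whether any patient who started a DMT in the SFU had follow-up ended because of it, with the DMT start date. Listing 16.2.1.1 (termination date and reason) and Listing 16.2.1.9 (post-treatment medications) are already planned, so the only addition is the text that links them.
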